**Step 5: END**

6. End.

PCT_{50} and PCT_{90} for each participant will then be estimated using the formulas described previously in this section. Individual estimates of K and t_{lag} will be presented in [Listing 15](#). The following pseudocode will be used to fit cubic normal and tobit regression models and to calculate model-predicted values for each participant's log-parasite density data.

```

/* Cubic Regression with Predicted Values by Participant ID */
data clearance; set clearance;
time2=time**2; time3=time**3;
log_density=log(density);
run;
proc reg data=clearance;
model log_density=time time2 time3 / p;
  
```

```

by partid;
ods output OutputStatistics=predicted;
run;

/* Cubic Tobit Regression with Predicted Values by Participant ID */
data clearance; set clearance;
time2=time**2; time3=time**3;
log_density=log(density);
/*replace parasite density values = the lower limit for the variable with.*/
if density=LOD then lower=.;
else lower=log_density;
run;
proc lifereg data=clearance outest=OUTEST(keep=partid _scale_);
  model (lower, log_density) = time time2 time3 / d=normal;
  by partid;
  /*output mean of uncensored variable*/
  output out=OUT xbeta=Xbeta;
run;
data predict; merge out outest; by partid;
  lambda = pdf('NORMAL',Xbeta/_scale_);
  / cdf('NORMAL',Xbeta/_scale_);
  /*calculate mean of censored variable*/
  predict = cdf('NORMAL', Xbeta/_scale_)
    * (Xbeta + _scale_*lambda);
run;

```

Total parasite clearance by Day 2 will be a binary variable indicating whether total parasite clearance has occurred within the first 50 hours post-first dose of IV artesunate. Total parasite clearance will be determined using all thick blood smears collected within the 50 hours from the first dose of IV artesunate. Total parasite clearance by Day 2 will be determined for participants in the PD Analysis Population with any results of thick blood smears available within 50 hours after the first dose of IV artesunate.

The relationship between AUC_{0-12} , C_{max} , $t_{1/2}$ and T_{max} , and the time-to-event response variables of PCT_{50} and PCT_{90} will be analyzed using Cox proportional hazards regression. One Cox proportional hazards regression model will be fit for each response variable and DHA exposure parameter. Covariates in these models will include the appropriate exposure parameter as well as a subset of the covariates given in Section 6.4.

Covariate selection for these models will be aided by exploratory boxplots of PCT_{50} and PCT_{90} by covariate in Figure 212 and Figure 213, respectively.

Models fit for the sensitivity analysis of the secondary analysis for PCT_{50} and PCT_{90} using the subset of the PD Analysis Population who did not receive IV artesunate or other artemisinin-based therapy before enrollment will be of the same form as those fit in the secondary analysis for the respective time to percent reduction parameter and exposure parameter. Covariates included in each model fit for this sensitivity analysis will be those included in the respective secondary analysis model with effects that remain estimable in the sensitivity analysis subset. The type of model and covariates included for each analysis model will be presented in Table 26 by parameter (PCT_{50} or PCT_{90}) and PK exposure parameter for the PD Analysis Population and the subset of the PD Analysis Population that did not receive IV artesunate or other artemisinin-based therapy before enrollment.

The Cox proportional hazards regression cumulative hazard function for PCT_{50} and PCT_{90} given AUC_{0-12} , C_{max} , $t_{1/2}$, or T_{max} will have the same form as that given in Section 8.2.1.

Hazard ratios for PCT_{50} and PCT_{90} corresponding to a one-unit change in exposure parameters adjusted for other covariates included in the models will be presented with corresponding 95% confidence intervals in

Table 25. Forest plots of hazard ratios and 95% CIs by exposure parameter will be presented for PCT₅₀ and PCT₉₀ in [Figure 216](#) and [Figure 217](#), respectively.

The relationship between exposure parameters (AUC₀₋₁₂, C_{max}, t_{1/2}, and T_{max}) and the binary variable of total parasite clearance by Day 2 will each be analyzed using logistic regression models. Covariate selection (see Section [6.4](#) for a list of covariates that will be considered) for these models will be aided by exploratory stacked bar charts of total parasite clearance by Day 2 by covariate, presented in [Figure 214](#) for participants in the PD Analysis Population.

The logistic regression model for total parasite clearance by Day 2 (Y) and AUC₀₋₁₂, for example, would be

$$\text{logit}(\pi) = \alpha + \beta \text{AUC}_{0-12,i} + \eta^T X_i,$$

where $\pi = \text{Pr}(Y = 1 | \text{AUC}_{0-12,i}, X_i)$ is the probability of total parasite clearance by Day 2 adjusted for covariates X_i and $\text{AUC}_{0-12,i}$, α is the model intercept, β corresponds to the log odds ratio for a one unit increase in AUC₀₋₁₂ adjusted for other covariates, and η is a vector with components corresponding to the log odds ratio comparing levels of each additional included covariate holding AUC₀₋₁₂ and any other covariates constant. The logistic regression function for total parasite clearance by Day 2 and C_{max}, t_{1/2}, or T_{max} would be of the same form.

Models fit for the sensitivity analysis of the secondary analysis for total parasite clearance by Day 2 using the subset of the PD Analysis Population who did not receive IV artesunate or other artemisinin-based therapy before enrollment will be of the same form as those fit in the secondary analysis for total parasite clearance by Day 2 and the respective PK exposure parameter. Covariates included in each model fit for this sensitivity analysis will be those included in the respective secondary analysis model with effects that remain estimable in the sensitivity analysis subset. The type of model and covariates included for each analysis model will be presented in [Table 28](#) by PK exposure parameter for the PD Analysis Population and the subset of the PD Analysis Population that did not receive IV artesunate or other artemisinin-based therapy before enrollment.

Parasite density will be summarized by timepoint in [Table 23](#). The proportion of participants with total parasite clearance will be presented by timepoint in [Table 24](#). Individual parasite densities and parasite species identified from thick and thin blood smears, respectively, will be listed in [Listing 14](#).

Odds ratios for total parasite clearance by Day 2 corresponding to a one-unit change in exposure parameters adjusted for the confounding variable will be presented with corresponding 95% confidence intervals in [Table 27](#). Forest plots of odds ratios and 95% CIs for total parasite clearance by Day 2 by exposure parameter will be presented in [Figure 218](#).

The following pseudocode will be used to fit a logistic regression model for total parasite clearance by Day 2 and estimate the odds ratio for a one-unit increase in exposure along with its Wald confidence interval after adjusting for other covariates.

```
/* Fit Logistic Regression and Estimate Odds Ratio for Exposure Parameter */
proc logistic data=dataset(where=(population=p));
*catvars = any categorical covariates included in the model;
*refvalues = the value(s) to be used as the reference level for categorical
covariate(s);
class catvars(param=ref ref=refvalues);
*othercovars = any other covariates (including those specified in the class statement)
included in the model;
model D2totcl (event='Yes') = exposure othercovars;
by timepoint;
oddsratio exposure;
```

```
ods output oddsratiostwald = orest;
run;
```

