Thick and thin blood smears will be performed for quantification of *P. falciparum* parasitemia. Thick blood smears will be used for diagnosis and thin blood smears for typing the species of malaria parasites. Thick and thin blood smears for malaria diagnosis will be stained with Giemsa stain and read at 100X power light microscope. Parasites will be quantitated by counting the number of asexual *P. falciparum* parasites per 200 WBC using the patient's WBC count per μ L of blood. Samples for malaria diagnostics will be collected according to the following schedule post-first on-study dose of IV artesunate in hours: 0 (0-2 hour acceptable window), 6 (4-8 hour acceptable window), 12 (10-14 hour acceptable window), 24 (22-26 hour acceptable window), 36 (34-38 hour acceptable window) and 48 (46-50 hour acceptable window), and then parasitemia should be measured at least every 24 hours through Study Day 5 and until clearance. Measures of parasite clearance will be calculated from quantified parasite density.

Total parasite clearance is defined as having a thick blood smear that is negative for *P. falciparum*, i.e. a thick blood smear for which there are no detectable *P. falciparum* parasites per 200 WBC. The date and time of total parasite clearance will be defined as the collection date and time of the first thick blood smear to meet the definition of parasite clearance. Total parasite clearance by Day 2 will be defined as the indicator of whether total parasite clearance occurred within the first 50 hours post-first dose of IV artesunate. Further details of how total parasite clearance by Day 2 is determined are given in Section [8.2.2](#).

Additionally, parasite clearance half-life (PCT₅₀) and time to 90% reduction in parasitemia (PCT₉₀) will be estimated using the WorldWide Antimalarial Resistance Network (WWARN) parasite clearance estimator (PCE) algorithm [\[4\]](#). Details of how PCT₅₀ and PCT₉₀ are calculated are given in Section [8.2.2](#).

Additional variables that will be used in exploratory PD analyses will be defined in an addendum(s) to this SAP.

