8.2.2. Parasite Clearance

We will additionally perform secondary analyses to assess the relationship between measures of DHA exposure, again including AUC_{0-12} , C_{\max} , $t_{1/2}$ and T_{\max} , and measures of parasitemia clearance. The outcome response variables for these analyses are measures of parasite clearance calculated from parasite density, as measured by thick blood smear, including parasite clearance half-life (PCT_{50}), total parasite clearance by Day 2, and time to 90% reduction in parasitemia (PCT_{90}).

PCT_{50} and PCT_{90} will be estimated using the WWARN PCE algorithm [\[4\]](#). PCT_{50} is the time from first on-study dose needed for parasitemia to be reduced by half during the log-linear phase of parasite clearance, and can be calculated by $PCT_{50} = \log_e(2)/K$, where K is the first-order clearance rate constant. PCT_{90} is the time from first on-study dose needed for parasitemia to be reduced by 90% during the log-linear phase of parasite clearance, and can be calculated by $PCT_{90} = \log_e(10)/K$. The first-order clearance rate constant K is typically equal to the negative slope of the log-parasitemia-time linear relationship during the log-linear phase of parasite clearance.

PCT₅₀ and PCT₉₀ will be estimated using the parasite density per μL . The parasite density per μL will be calculated using the formula: Number of parasites per 200 WBCs \times 40 = asexual parasites / μL . The clearance rate constant K will be calculated using the following steps according to the WWARN PCE algorithm [4] for each participant separately.

1. Perform data cleaning. Data cleaning will proceed in order as follows:
 - a. Removal of data from recurrences of parasitemia including any measurements after 7 days, measurements after a time when 2 measurements are >24 h apart, and data after the last measured zero parasitemia if the positive measurements before and after this measurement are separated by >24 h are removed.
 - b. Removal of all trailing zeros after the last nonzero parasitemia except the first zero.
 - c. Removal of repeated parasitemia measurements $<100/\mu\text{L}$ and data that fall between them.
 - d. Replacement of the first zero parasitemia measurement directly after the last positive parasitemia with the limit of detection ($40/\mu\text{L}$ [4]).
 - e. Removal of extreme values outside of the range ($0, 3 \times 10^6$) or measurements with times below zero.

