where P_i is the participant's parasitemia at the i th time, t_i is the i th time, and e_i is the measurement error term for the i th measurement.

a. If none of the conditions in Steps 2 or 3 are met, then fit models to the natural log-parasitemia versus time data as described in the following figure provided in [4].

b. If none of the criteria in Step 2 are met but the criteria in Step 3 is met, fit tobit linear regression if a zero parasitemia measurement has been recorded for the participant or normal linear regression otherwise.

c. If any of the criteria in Step 2 are met, K and the duration of the lag phase (t_{lag}) cannot be estimated, so proceed to Step 6 below.

5. Estimate K and t_{lag} according to the following figure given in [4].

Step 1: Find Best model

Best model is defined as the model with the smallest AIC or $\text{RSS}_{\text{shared}}$ among fitted models, where appropriate.

Step 2: Identify possibly convex models

[figure not shown]
Possibly convex models are quadratic or cubic models with negative concavity somewhere over the time domain.

Step 3: If model is NOT possibly convex:

$K = -b_1$; $t_{\text{lag}} = 0$; GO TO **Step 5**

Step 4: If model is possibly convex

- 4.1 For each log-parasitaemia predicted by the Best model y_i (but excluding any measured zero parasitaemias), calculate slope S_i between this point and the preceding predicted value
- 4.2 Find the most negative slope, S_{max}
- 4.3 Calculate normalised slopes $S_n = S / S_{\text{max}}$
- 4.4 Find clearance rate constant using the chart below

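### The tobit code for parasite clearance censors an observed single-parasite smear as if it were negative, because both carry the value 40/µL

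*SAP*

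**What the plan says.** SAP section 8.2.2 derives PCT50 and PCT90 from a clearance rate constant K, fitted to each child's log parasite density over time. Four statements matter here.

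- **Density.** It is "calculated using the formula: Number of parasites per 200 WBCs" times 40.
- **Zeros.** Cleaning step 1d is the "Replacement of the first zero parasitemia measurement directly after the last positive parasitemia with the limit of detection", given as 40/µL.
- **When tobit is used.** Where the lag phase cannot be estimated (step 4b), the instruction is to "fit tobit linear regression if a zero parasitemia measurement has been recorded for the participant or normal linear regression otherwise". Otherwise (step 4a), linear, quadratic and cubic tobit or normal models are candidates.
- **Censoring.** In the cubic tobit code, "if density=LOD then lower" becomes missing, "else lower=log_density" applies to every other record, and the call is "model (lower, log_density) = time time2 time3 / d=normal". A missing lower bound makes the record left-censored at log 40.

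SAP section 4.5.1 defines total parasite clearance by a negative smear, "a thick blood smear for which there are no detectable" parasites per 200 WBC. A count of one is therefore positive. The same section, and Protocol section 8.3.1, say density is quantified with the patient's own WBC count, not with a fixed factor.

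**The concern.** Left-censoring is right for a substituted zero, where all that is known is that the density was at or below the detection limit. It is wrong for a smear on which a parasite was seen and counted. The code has no variable that separates the two and relies on the density value to do so. Under the ×40 formula that value is the same for both.

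A tail of one parasite followed by a negative smear then yields two censored points instead of one, and the last measured positive loses its value. PCT50 and PCT90 are direct transforms of K. They feed eight Cox models (two responses × four exposure parameters) and the matching sensitivity models. K is also listed child by child in Listing 15. A programmer following the code would produce the error without any warning.

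**Working it through.** **1. The collision.** One parasite per 200 WBC × 40 = 40/µL. The step 1d substitute is 40/µL. The match is exact.

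**2. Does cleaning remove it?** Step 1c removes only repeated values below 100/µL, and it runs before the substitution in 1d. A single 40/µL reading followed by a zero therefore survives. No later rule is aimed at an isolated count of one.

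**3. Effect in a linear tobit.** Model: log density = β0 + β1·t + e; K = −β1; PCT50 = ln 2 / K. Each illustrative profile (counts per 200 WBC at 0, 6, 12, 24, 36 and 48 h, as far as it runs) was fitted twice, with only the zero censored and as coded.

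| Counts | PCT50, zero only | PCT50, as coded | Change in K |
|---|---|---|---|
| 1500, 900, 150, 10, 1, 0 | 3.25 h | 3.10 h | +5% |
| 1000, 500, 60, 1, 0 | 2.31 h | 2.16 h | +7% |
| 800, 200, 40, 5, 1, 0 | 3.74 h | 3.27 h | +14% |
| 2500, 900, 60, 3, 1, 0 | 3.00 h | 2.38 h | +26% |

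The direction is systematic here. Censoring a late observed point removes its upward hold on the line and leaves only a downward pull.

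**4. How often, and how much on average.** The documents give no clearance data, so these are simulations on the planned smear times under assumed inputs, fitted with the linear tobit.

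- Half-life 2.5 or 3.5 h, log SD 0.3 or 0.6, median baseline 40,000/µL: 28–37% of eligible profiles held a single count of one. Among those fitted, K rose in 253 of 253. The median ratio was 1.05–1.10 and the maximum 1.25–1.60, depending on scenario.
- Median half-life 2.5–5 h, median density 30,000–100,000/µL: 27–32% affected, median rise in K 5–7%, 90th percentile 15–30%.

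**5. Effect under the SAP's model selection.** Step 3 sends a profile to the linear-only branch if it has fewer than three measurements, or a gap of more than 14 h, in the first 24 h. With smears at 0, 6, 12 and 24 h the largest gap is 12 h, so on-schedule profiles go to step 4a. For 2500, 900, 60, 3, 1, 0 the AICs are:

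| Censoring | Linear | Quadratic | Cubic |
|---|---|---|---|
| Zero only | 16.4 | 13.4 | 15.1 |
| As coded | 9.1 | 11.1 | 12.4 |

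With the zero alone censored, the quadratic wins. Its curvature is positive, so the SAP's rule for models that are not possibly convex applies, K = −b1. If b1 is the best model's coefficient, K = 0.377/h. As coded, the linear model wins with K = 0.291/h. The ratio is 0.291 / 0.377 = 0.77, a fall of about 23%. If b1 instead means the linear slope, the comparison is ln 2 / 3.00 = 0.231 against 0.291/h, a rise of 26%. The text available does not settle which is meant.

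Simulated quadratic fits (half-life 3 h, log SD 0.4, K taken as the steepest predicted slope, no model selection) gave a median ratio of 1.05 without a lag, with 56% above 1. With a 6 h lag the median was 1.51, and all were above 1.

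**6. The other density rule.** With the patient's own WBC, one parasite is WBC/200: 20, 30, 40, 50 or 75/µL at 4,000, 6,000, 8,000, 10,000 or 15,000 WBC/µL. The exact match then occurs only at 8,000.

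**The case against.** Four points have force.

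**Direction.** A reader might infer that clearance is overestimated in every affected child. That holds for the linear tobit only. The planned schedule leads to step 4a, and working step 5 shows a profile whose K may fall instead. This objection stands. It does not reach children whose actual smear times trigger the linear-only branch. Under the allowed windows, the interval between the 12 h and 24 h smears can be as long as 26 − 10 = 16 h.

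**Size.** The +26% profile is near or above the simulated 90th percentiles, so it shows what can happen and not what is typical. In a linear-tobit simulation over all profiles, with 23–31% affected, mean K rose 2–3%, the median ratio was 1.00 and the rank correlation between the two codings was 0.97–0.99. Cox models depend on the ordering of times. A reader might infer that every exposure–clearance test is distorted. Nothing in the documents or the calculations shows that, and no link between the error and DHA exposure has been demonstrated.

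**Own-WBC density.** One might think that matching on 40 fails under that rule too. It largely does not, because only replaced zeros would then carry exactly 40, except at a WBC of 8,000. The defect therefore depends on the ×40 rule. That rule is, however, the one section 8.2.2 states for these two endpoints.

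**Only pseudocode.** A careful analyst could read step 1d and set a flag. But the SAP says this code will be used, and it contains the only censoring rule given.

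**Conclusion.** Wrong as written. Under the ×40 formula, the tobit code treats a measured positive of one parasite per 200 WBC as a negative smear. That follows from the SAP alone and needs no assumption.

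The reach is limited. It needs a recorded zero and a smear of exactly one parasite. Last positives of two or more, profiles without a zero, total clearance by Day 2 and the primary analysis are untouched. The share affected (roughly a quarter to a third of estimable profiles) and the median rise in K of about 5–10% rest on assumed half-life, baseline density and noise, and the rise applies to the linear tobit. Under linear, quadratic or cubic selection the error can switch the chosen model and shift K in either direction. Its effect on the Cox results for PCT50 and PCT90 is unquantified, and its size in this trial cannot be found from the documents. The documents support an error in handling observed data, but not a general claim that clearance is overestimated.

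**What to change.** At step 1d, create a flag from the raw count before substitution (`zero_replaced=1` for the replaced zero). In every tobit fit, whether linear, quadratic or cubic, set `lower` to missing only when that flag is 1, and to the log density otherwise. Never infer censoring from the density value.

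Also state one density formula for PCT50 and PCT90, reconciling the ×40 rule in SAP section 8.2.2 with the patient's-own-WBC rule in SAP section 4.5.1 and Protocol section 8.3.1. If the own-WBC rule is kept, say how the 40/µL limit applies when a single parasite computes to less than 40/µL, as it does at any WBC below 8,000. The flag is needed under either rule.

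The coding cost is one variable and one changed line, and it leaves the coding of all other records unchanged. Choosing the density rule is a short SAP clarification, best made before the clearance models are run.

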7.3 Follow-up

Details of the schedule of events, including laboratory analyses, are included in the summary of study procedures (Section 8.1) and Schedule of Events (Table 19.1). If a subject is discharged before study day 7, the required follow-up visits are study day 7, 14, 28, and 183.

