Notes: N = Number of participants in each analysis population or subset for which thick blood smear results are available within 50 hours after the first dose of IV artesunate. N* = Number of participants in each analysis population or subset with estimable PK exposure parameter and for which thick blood smear results are available within 50 hours after the first dose of IV artesunate.

CI = Confidence interval.

Total parasite clearance by day 2 is determined using blood smears collected within 50 hours post-first dose of IV artesunate.

^a Odds ratios and 95% CIs are estimated using a logistic regression model adjusted for the PK exposure parameter and other covariates. See [Table 28](#) for the covariates included in each model.

Table 28: Model Specifications for Assessments of Relationships between Total Parasite Clearance by Day 2 and Exposure Parameters by Exposure Parameter and Analysis Population

[Implementation Note: Model Type will be Logistic Regression. Covariates Included in the Model will at minimum include Exposure Parameter and Actual Time of Collection, but may also include Sex, Weight Group, Receipt of IV Artesunate or Other Artemisinin-Based Therapy Before Enrollment, Receipt of Concomitant Medications, and Receipt of Oral ACT included as covariates.]

Analysis Population	PK Exposure Parameter	Model Type	Covariates Included in the Model
PD Analysis Population (N=X)	AUC ₀₋₁₂ (N*=X)		
	C _{max} (N*=X)		
	T _{max} (N*=X)		
	t _{1/2} (N*=X)		
PD Analysis Population, No Prior IV Artesunate or Other Artemisinin-Based Therapy Subset (N=X)	AUC ₀₋₁₂ (N*=X)		
	C _{max} (N*=X)		
	T _{max} (N*=X)		
	t _{1/2} (N*=X)		

Notes: N = Number of participants in each analysis population or subset for which thick blood smear results are available within 50 hours after the first dose of IV artesunate. N* = Number of participants in each analysis population or subset with estimable PK exposure parameter and for which thick blood smear results are available within 50 hours after the first dose of IV artesunate.

Total parasite clearance by day 2 is determined using blood smears collected within 50 hours post-first dose of IV artesunate.

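### Day-2 parasite clearance scores a child with no negative smear and no late smear as not cleared, and the Table 28 note adds an undefined collection-time covariate

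*SAP*

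**What the plan says.** - **Outcome.** SAP 4.5.1 defines Day-2 clearance as the "indicator of whether total parasite clearance occurred within the first 50 hours post-first dose of IV artesunate". Clearance is dated to the "first thick blood smear to meet the definition of parasite clearance", so one negative smear at any time up to 50 hours scores *yes*. There is no third level for unknown.
- **Who is scored.** SAP 8.2.2 scores PD-population children "with any results of thick blood smears available within 50 hours after the first dose of IV artesunate". The notes to Tables 27 and 28 repeat this, counting children "for which thick blood smear results are available within 50 hours after the first dose of IV artesunate".
- **Planned late smears.** SAP 4.5.1 lists "24 (22-26 hour acceptable window), 36 (34-38 hour acceptable window) and 48 (46-50 hour acceptable window". Smears then continue at least daily through Study Day 5 and until clearance. The 50-hour limit is the upper edge of the 48-hour window (48 + 2).
- **Missing data.** SAP 6.5 does not impute secondary responses, and it restricts each analysis to children whose response was measured at the timepoint concerned.
- **After discharge.** Protocol 7.3: "If a subject is discharged before study day 7, the required follow-up visits are study day 7, 14, 28, and 183".
- **Covariates.** The Table 28 note says: "Covariates Included in the Model will at minimum include Exposure Parameter and Actual Time of Collection". The list in SAP 6.4, the logistic equation and the pseudocode in 8.2.2 contain no collection time. SAP 15 mentions measurement time only as an option, for linear and polynomial models.

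**The concern.** Eligibility for scoring is set by any smear, but the outcome concerns what had happened by 50 hours. If a child's smears are all positive and stop at about 24 hours, nothing was observed about clearance between then and 50 hours. The child is nevertheless in the denominator, and *no* is the only score available.

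The error would matter most if the missing smears were related to exposure. IV treatment can end after 24 hours, and a child discharged before Day 7 has no required visit until Day 7. If higher exposure brought faster recovery and earlier discharge, unobserved outcomes coded as failures would collect at high exposure and work against the association under study.

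The Table 28 note raises a separate problem. If the required collection time is that of the smear that decided the outcome, it is early for cleared children and late for the others. Adjusting for it would then adjust for the outcome itself.

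**Working it through.** The documents give no sample size, power or event rate for this endpoint, so there is no plan figure to reproduce.

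**1. The rule case by case**

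| Smears in 0–50 h | Score under 8.2.2 | Status by 50 h observed? |
|---|---|---|
| Any negative | Yes | Yes |
| None negative, last at 46–50 h | No | Yes, to within the window |
| None negative, last at about 24 h | No | No |

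The third row is the defect. SAP 6.5 would leave such a child out; 8.2.2 puts the child in.

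**2. Effect on the cleared share**

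Let m be the share with no smear after 24 h (loss at random), and p24 and p48 the proportions negative by 24 h and 48 h.

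- Share scored cleared = (1 − m)·p48 + m·p24, so the understatement is m·(p48 − p24).
- With p48 − p24 = 0.40 (assumed), this is 2, 4 and 8 percentage points at m = 5%, 10% and 20%.
- With log-normal clearance times, median 36 h and log-SD 0.45 (assumed): p24 = Φ(ln(24/36)/0.45) = Φ(−0.901) = 0.184 and p48 = Φ(ln(48/36)/0.45) = Φ(0.639) = 0.739. The difference is 0.555, giving 2.8, 5.6 and 11.1 points.

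**3. Effect on the exposure odds ratio**

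Simulated logistic regression on the SAP smear schedule, N = 80, with the same clearance assumptions. Cells show the odds ratio and, in brackets, the share of trials rejecting the null. The late-smear rule scores only children who have the late smears and sets all others to missing.

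| True effect | Loss after 24 h | Complete data | SAP rule | Late-smear rule |
|---|---|---|---|---|
| Present | Random 10% | 2.66 (0.937) | 2.34 (0.897) | 2.63 (0.906) |
| Present | Random 20% | 2.63 (0.931) | 2.18 (0.855) | 2.66 (0.848) |
| Present | Exposure-linked 10% | 2.64 (0.929) | 1.93 (0.701) | 2.65 (0.878) |
| Present | Exposure-linked 20% | 2.58 (0.921) | 1.62 (0.488) | 2.61 (0.817) |
| None | Random 10% | 0.98 (0.041) | 0.98 (0.040) | 0.97 (0.038) |
| None | Random 20% | 0.99 (0.043) | 0.99 (0.042) | 0.99 (0.039) |
| None | Exposure-linked 10% | 0.99 (0.033) | 0.81 (0.114) | 1.00 (0.038) |
| None | Exposure-linked 20% | 1.00 (0.049) | 0.73 (0.239) | 1.00 (0.051) |

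Step 2 agrees with the simulated cleared shares under random loss and no effect. At 10%, 0.9 × 0.739 + 0.1 × 0.184 = 0.684 (simulated 0.683). At 20%, 0.8 × 0.739 + 0.2 × 0.184 = 0.628 (simulated 0.626).

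With no effect and exposure-linked loss of 10% or 20%, the SAP rule rejects 8.6% or 16.1% at N = 46 (enrolment when the planned period ended, SAP 5) and 14.0% or 26.4% at N = 100. A separate run at N = 75 gave 13% and 23%.

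**4. Keeping early-negative children who lack a late smear**

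This drops early non-clearers but keeps early clearers. At 20% random loss the cleared share becomes 0.628 / (0.8 + 0.2 × 0.184) = 0.628 / 0.837 = 0.750, against a true 0.739. Under exposure-linked loss of 10% or 20%, the odds ratio is 2.75 or 2.81 with an effect, and 1.03 or 1.05 without. In a further null run at N = 75, with 20–30% exposure-linked loss of the 48 h smear alone, the log odds ratio was +0.12 to +0.22 with 4–7% rejection. The SAP rule gave −0.22 to −0.31, and the symmetric rule about 0.

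**5. The collection-time covariate (N = 80, true effect present)**

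- Read as time of first negative smear if cleared and last smear otherwise: the odds ratio falls from 2.62 to 1.80 and power from 0.90 to 0.31, with essentially no missing smears.
- Read as time of the last smear in the window for every child: the odds ratio is unchanged at 2.65 with complete smears, and 2.7–2.75 with 10–20% of late smears missing.

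**The case against.** The plan schedules smears at 36 and 48 hours and at least daily afterwards, so a child still positive at 24 hours with no later smear has missed two planned collections. Nothing in the documents supports a loss of 10–20%. Fast recoverers are also the children most likely to be negative already and correctly scored. Table 24 shows denominators by timepoint and Listing 14 lists every smear, so gaps would be visible. This is one of several secondary outcomes without multiplicity adjustment, and Table 27 reports odds ratios and intervals without p-values.

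The point about size stands: it is conditional on assumed loss. The rest does not remove the defect. A visible gap still enters the model as a failure, and a shifted interval misleads with or without a p-value.

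Four stronger readings are tempting but unsupported:

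- *Every child without a smear after 24 hours counts as not cleared.* One negative at or before 24 hours scores yes.
- *The SAP states that missing equals failure.* It does not; this follows from the any-smear denominator and the two-level outcome.
- *The two clocks create a further gap.* SAP 4.5.1 does say "Samples for malaria diagnostics will be collected according to the following schedule post-first on-study dose of IV artesunate in hours", while the 50 hours run from the first dose of all. But doses fall at 0, 12 and 24 hours from first dose (SAP 4.1, 4.4.5). A first on-study dose at 12 h gives smears at 12, 18, 24, 36, 48 and 60 h; one at 24 h gives 24, 30, 36, 48, 60 and 72 h. Both include 48 h. Only off-schedule dosing opens a gap.
- *Table 28 certainly conditions on the outcome.* The SAP never says which smear's time is meant, and step 5 shows that the answer depends on this. The same phrase appears under Tables 22 and 26, where no single collection time exists, which suggests carried-over text.

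**Conclusion.** The concern holds in this limited form and should be fixed before analysis. SAP 8.2.2 and the notes to Tables 27 and 28 impute failure, without saying so, for children who have no negative smear and no late smear, against SAP 6.5. Under random loss the odds ratio is pulled toward 1 and the null rejection rate is unaffected. Under loss that rises with exposure the attenuation is larger, and with no true effect the estimate passes below 1, with rejection of about 11–24% at N = 80.

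The direction follows from the rule together with the loss pattern. The size rests on the assumed 10–20% loss, a 36-hour median clearance time and loss driven by exposure alone. None of these comes from the documents, and if late smears are nearly complete the effect is small.

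The collection-time note contradicts SAP 6.4, the logistic equation and the pseudocode on any reading. Whether it also does harm depends on a definition that is not given.

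**What to change.** 1. **Preferred:** analyse time from first dose to first negative smear as interval-censored, between the last positive and first negative smear, with children never seen negative censored at their last smear. This uses every child. It assumes that smears stop for reasons unrelated to clearance once the model's covariates are accounted for. The result is no longer an odds ratio, so the Table 27 shell changes.
2. **If the binary outcome is kept:** score it only for children with a smear 46–50 hours after first dose, applying that requirement equally to cleared and uncleared children. Set the others to missing, report the count, and align 8.2.2 and the notes to Tables 27 and 28 with SAP 6.5.
3. If early-negative children without a late smear are kept as cleared, state the small upward bias and show that version as a sensitivity analysis.
4. Delete the collection-time covariate from the notes to Tables 22, 26 and 28.

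The cost is SAP wording and one derivation. Under the binary version some children become non-evaluable. At 20% random loss its power matches the SAP rule (0.848 against 0.855), so the gain there is a correct estimate. At 20% exposure-linked loss power rises from 0.488 to 0.817.
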